4.7.2. Clinical Laboratory Tests

Hematology, chemistry, urinalysis, serology, and coagulation results will be summarized and listed.

Clinical laboratory assessments are listed in Table 4.

Table 4: Clinical Laboratory Evaluations

Blood chemistry	Albumin, alkaline phosphatase, anion gap, total bilirubin (indirect and direct), bicarbonate, calcium, chloride, total cholesterol, creatinine, gamma GT, globulin, glucose, lactate dehydrogenase, phosphorus, potassium, total protein, AST, ALT, sodium, triglycerides, urea, and uric acid
Coagulation	d-Dimer, PT, INR, and PTT; anti-phospholipid antibodies (screening only)
Serology	HbsAg, HbsAb, HbcAb and HCVAb, HIV
Hematology	Absolute neutrophil count, differential, hematocrit, hemoglobin, MCH, MCHC, MCV, platelet count, erythrocytes, leukocytes (basophils, eosinophils, lymphocytes, monocytes, neutrophils)
Urinalysis	Bilirubin, blood, color, glucose, ketone, leukocytes, nitrite, pH, protein, specific gravity, turbidity, urobilinogen. If blood, leukocytes, nitrite, or protein are out of range, then microscopic exam (includes bacteria, cast, crystals, epithelial cells, red blood cell, white blood cell) will be automatically run.
Urine drug screen	Amphetamines (includes methamphetamines and ecstasy/MDMA), cocaine metabolites, opiates (includes heroin, codeine, and oxycodone) methadone, phencyclidine
Other	Serum pregnancy test

Note: All laboratory tests will be collected locally.

ALT = alanine aminotransferase, AST = aspartate aminotransferase, GT = glutamyl transferase, HbsAg = hepatitis B surface antigen, HbsAb = hepatitis B surface antibody, HbcAb = hepatitis B core antibody; HCVAb = hepatitis C antibody; HIV = human immunodeficiency virus, INR = MCH = mean corpuscular hemoglobin, MCHC = mean corpuscular hemoglobin concentration, MCV = mean corpuscular volume, MDMA = methylenedioxymethamphetamine, PT = prothrombin time; PTT = partial thromboplastin time

The data collected in different units were converted to SI units (the International System of Units) for summary. The following summaries will be provided.

- Numeric laboratory values will be summarized as descriptive statistics for both actual value and change from baseline (post baseline minus baseline) by week. If lab values are recorded as <xx, the limits of xx will be used for summary.
- Shift table summarizing subject incidence of laboratory normal range (Low, Normal, High) at baseline contrasted with lowest or highest post baseline. Parameters with bidirectional abnormality (low and high) will be presented by post baseline lowest and highest. The shift table will include subjects without data so that all subjects in the SAF analysis set at baseline will be included.

Neutrophils

The incidence of neutropenia by maximal grade (lowest Neutrophils value reported) during the treatment period will be summarized. The 4 grades are defined as below:

- Grade 1: $\geq 1.5 \cdot 10^9 / L low limit of normal range$
- Grade 2: $>=1-1.5 \cdot 10^9/L$
- Grade 3: $>=0.5 1.10^9/L$
- Grade 4: $< 0.5 \ 10^9/L$

For subjects with Grade 3 or 4 neutropenia, a listing with the individual neutropenia counts, WBC, platelet counts, lymphocytes and hemoglobin at each visit (including unscheduled visits for re-test) will be provided. In addition, the neutropenia counts at each scheduled visit during the study will be summarized by treatment group.

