- 10. Clinically significant active infection, including signs/symptoms suggestive of infection, any significant recurrent or chronic infection (including positive hepatitis C virus antibody), or any episode of infection requiring hospitalization or treatment with IV antibiotics within 12 weeks before screening, or treatment with oral anti-infectives within 14 days prior to the first dose of investigational product. Subjects with any opportunistic infection within 6 months before screening will be excluded from the study.
- 11. Presence of symptoms indicative of COVID-19 infection (according to the opinion of the Principal Investigator) unless a PCR test for COVID-19 has been reported as negative within the previous 7 days or is acquired prior to randomization.
- 12. Subjects at a high risk of infection (e.g., history of hereditary or acquired immune deficiency disorder), a history of an infected joint prosthesis at any time with that prosthesis still in situ, leg ulcers, indwelling urinary catheter, or persistent or recurrent chest infections.
- 13. Subjects testing positive for human immunodeficiency virus infection. HIV test will not be required if a subject had a previously documented negative HIV result within 8 weeks screening.

- 14. Subjects with chronic active hepatitis B infection as defined below will be excluded from the study:
 - a. Hepatitis B surface antigen positive.
 - b. Hepatitis B anti-core antibody positive but anti-surface antibody negative.
- 15. Positive (or 2 indeterminate) QuantiFERON® test results unless confirmation of prior completion of appropriate treatment for latent TB and no evidence of active TB (when possible, test should be performed at least 4 weeks after receiving an mRNA COVID-19 vaccine).
- 16. History of thromboembolic event, a significant risk of future thromboembolic events (defined as a definitive diagnosis of thrombophilia OR an unstable condition associated with an increased incidence of thrombosis, such as atrial fibrillation or anti-phospholipid syndrome). All history of thrombosis should be approved by the medical monitor.
- 17. Laboratory values meeting the following criteria within the screening period (prior to randomization) of investigational product:
 - a. Serum aspartate aminotransferase $> 3 \times$ upper limit of normal (ULN);
 - b. Serum alanine aminotransferase $> 3 \times ULN$;
 - c. Total bilirubin $> 2 \times ULN$;

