 - d. Estimated glomerular filtration rate by simplified 4-variable Modification of Diet in Renal Disease formula < 40 mL/min/1.73 m²;
 - e. Absolute neutrophil count $< 1,500/\mu L;$
 - f. Hemoglobin < 9 g/dL;
 - g. Total white blood cell count $< 2,500/\mu L$;
 - h. Platelet count $< 150,000/\mu L$;
 - i. Absolute lymphocyte count $< 800/\mu L$.
- 18. Known history of allergy or reaction to any component of the KPL-404 or placebo formulation and/or other products in the same class.
- 19. History of cancer within the last 5 years from screening, except for basal and squamous cell carcinoma of the skin or in situ carcinoma of the cervix treated and considered cured.
- 20. History of clinically significant (per Investigator's judgment) drug or alcohol abuse within the last 6 months.
- 21. History of any of the following cardiovascular conditions:
 - a. Moderate to severe congestive heart failure (New York Heart Association class III or IV);
 - b. Recent (within past 6 months) cerebrovascular accident, myocardial infarction, coronary stenting;
 - c. Uncontrolled hypertension as defined by a confirmed systolic blood pressure > 160 mmHg or diastolic blood pressure > 100 mmHg.
- 22. Clinically relevant or significant electrocardiogram (ECG) abnormalities, including ECG with QT interval corrected for heart rate (QTc) > 500 msec.

23. Any condition that, in the opinion of the Investigator, could interfere with evaluation of the investigational product or interpretation of subject safety or confound the results of the study.

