3.1. Baseline Value and Change from Baseline

The baseline value of efficacy parameters is defined as the last non-missing value before randomization and prior to the first dose of study medication otherwise specified.

For safety endpoints, baseline is defined as the last non-missing value obtained prior to the first dose unless otherwise specified.

Change from baseline, where applicable, will be calculated at each visit over time as the post-baseline evaluation minus the baseline evaluation.

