4.7.1. Adverse Events

Adverse events will be mapped to PT and SOC using the most up to date MedDRA of the version at database lock. A treatment-emergent AE (TEAE) is defined as any event not present before exposure to study drug or any event already present that worsens in either intensity or frequency after exposure to study drug during treatment period. Furthermore, if an AE cannot be determined as treatment-emergent due to incomplete/missing date, conservatively, it will be considered as treatment emergent and included in the summary tables. A post-treatment AE is defined as any AE that occurs during the off-treatment period (see the definition of treatment duration in Section 4.5).

The following TEAE summaries will be summarized by treatment group.

- Any TEAEs
- Drug-related TEAEs
- TEAE by maximum severity (mild, moderate, severe)
- Serious TEAEs (SAEs)
- Drug related serious TEAEs
- TEAEs leading to dose interruption
- TEAEs leading to treatment discontinuation
- TEAEs leading to study discontinuation
- Death
- TEAEs of special interest (AESI)

A subject experiencing the same AE multiple times will be counted only once for that preferred term. Similarly, if a subject experiences multiple AEs (preferred terms) within the same system organ class, then that subject will be counted only once for that system organ class. When summarizing by severity and relationship, only the event with highest severity or relationship will be counted. All AEs will be presented by SOC and preferred terms.

In addition, post-treatment AEs and SAEs will also be summarized.

All AEs will be displayed in by-subject listings.

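### SAP 4.7.2 tabulates neutropenia from the lowest on-treatment count with no baseline reference, so unchanged low counts at entry are mixed with on-treatment worsening (minor, cheap to improve)

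*SAP*

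**What the plan says.** The Neutrophils paragraph of SAP 4.7.2 plans a dedicated summary: "The incidence of neutropenia by maximal grade (lowest Neutrophils value reported) during the treatment period will be summarized". It defines four grades in ×10⁹/L: Grade 1 from 1.5 up to the lower limit of normal, Grade 2 from 1 to 1.5, Grade 3 from 0.5 to 1, and Grade 4 below 0.5. No value is given for the lower limit of normal. The paragraph does not mention a baseline grade.

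Protocol 7.2, criterion 17, excludes subjects with "Laboratory values meeting the following criteria within the screening period (prior to randomization) of investigational product". Item e is "Absolute neutrophil count $< 1,500" per µL.

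Other parts of the SAP do refer to baseline:

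- SAP 3.1: "For safety endpoints, baseline is defined as the last non-missing value obtained prior to the first dose unless otherwise specified".
- SAP 4.7.1 defines a treatment-emergent event as "any event not present before exposure to study drug or any event already present that worsens in either intensity or frequency after exposure".
- SAP 4.7.2 plans change from baseline by week for numeric laboratory values, and this table: "Shift table summarizing subject incidence of laboratory normal range (Low, Normal, High) at baseline contrasted with lowest or highest post baseline".

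For neutrophils, SAP 4.7.2 also plans counts at each scheduled visit by treatment group, and a visit-level listing for subjects with Grade 3 or 4.

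**The concern.** The sponsor has given neutropenia its own table, presumably to learn whether counts fall on KPL-404. As specified, a reader of that table cannot tell a subject whose count fell on treatment from one who arrived with a low count and kept it. The lowest count that entry allows is exactly where Grade 1 begins, so the eligibility rule lets the whole Grade 1 band into the study.

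The arms are small, so a few subjects with low counts at entry, unevenly spread by chance, could make a treatment difference at Grade 1 look larger or smaller than it is.

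**Working it through.** The plan states no figure on this point, so there is none to reproduce. The check has four steps.

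**1. Units.** 1,500/µL × 10⁶ µL/L = 1.5 ×10⁹/L. The entry floor therefore equals the Grade 1 floor. Entry is judged on the screening value and baseline is the last pre-dose value, so a baseline below 1.5 (Grade 2) is also possible.

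**2. The rule applied to example subjects.** Lower limit of normal (LLN) assumed to be 1.8 or 2.0; both give the same result.

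| Baseline → lowest on treatment | Grade at baseline → worst | In the SAP table? | Grade worsened? | Low/Normal/High shift |
|---|---|---|---|---|
| 1.6 → 1.6 | 1 → 1 | yes | no | Low → Low |
| 1.6 → 1.4 | 1 → 2 | yes | yes | Low → Low |
| 2.5 → 1.7 | 0 → 1 | yes | yes | Normal → Low |

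The first two subjects differ in what happened on treatment but share a shift-table cell. With an LLN of 1.5 or less, the Grade 1 band is empty and 1.6 → 1.6 is not counted at all. The SAP's own Grade 1 definition presumes an LLN above 1.5.

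**3. Size.** The documents give no neutrophil distribution, so all of the following is assumed: log-normal counts with median 4.0, 4.7 or 5.5 ×10⁹/L; log-scale SD 0.35 between and 0.20 within subjects; LLN 1.8 or 2.0; no drug effect. Each simulated subject has a screening count (kept only if at least 1.5), a baseline count, and four post-baseline counts (Weeks 2, 4, 8 and 12, as in the Schedules of Activities). Two million subjects were drawn per setting.

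Share not worsened = (any grade − grade worse than baseline) / any grade. For example, (9.20 − 7.20) / 9.20 = 22%. Differences and shares were taken before rounding.

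| Median, LLN | Any grade, % | Worse than baseline, % | Difference, points | Share not worsened |
|---|---|---|---|---|
| 4.0, 2.0 | 9.20 | 7.20 | 2.00 | 22% |
| 4.0, 1.8 | 5.28 | 4.40 | 0.88 | 17% |
| 4.7, 2.0 | 4.12 | 3.35 | 0.78 | 19% |
| 4.7, 1.8 | 2.13 | 1.83 | 0.30 | 14% |
| 5.5, 2.0 | 1.62 | 1.35 | 0.26 | 16% |
| 5.5, 1.8 | 0.76 | 0.67 | 0.09 | 12% |

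Of the cases that did not worsen, 72–93% were Grade 1, nearly all the rest were Grade 2, and almost none were Grade 3–4.

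**4. In subjects.** Planned enrollment (protocol 11.1) is 25 per arm in Cohort 3, and 24 and 16 in Cohort 4. In a 25-subject arm the expected number of unworsened cases is 25 × 0.0009 = 0.02 to 25 × 0.0200 = 0.5. One such subject moves the arm's rate by 1/25 = 4.0 points, 1/24 = 4.2 points or 1/16 = 6.3 points.

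**The case against.** A table of worst on-treatment grade is a legitimate display and reports what its label says. A reader might infer that the SAP presents these subjects as new neutropenia. It does not: the paragraph says neither new nor treatment-emergent. SAP 4.7.4 also uses incidence for an absolute cut-off, QTcF above 500 msec, with no baseline reference. The treatment-emergent definition in 4.7.1 governs a different table. This part of the objection stands.

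The baseline information is also available elsewhere: in the shift table, the change-from-baseline and by-visit summaries, the Grade 3–4 listing, and the by-subject listings of all safety data (SAP 3). This stands in part. The listings would let someone reconstruct the answer subject by subject. But no planned summary separates an unchanged Grade 1 from a worsening one, and the dedicated neutrophil listing covers only Grades 3 and 4.

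Two other strong readings are tempting. One is that up to 29% of tabulated cases are spurious. That figure is the share already below normal at baseline in the most affected setting, and some of those subjects worsened and belong in the table. The other is that the table should count only worsened grades. That would remove persistently low counts from view, including a Grade 2 baseline that stays Grade 2. Nor would it remove most chance imbalance, because 78–88% of the simulated cases with no drug effect did worsen by grade.

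Finally, protocol 11.7 plans no inferential safety analysis, and randomization balances entry counts on average. Both points stand and keep the matter minor.

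**Conclusion.** The point holds as a gap in presentation. The neutropenia summary mixes counts that were low before dosing with counts that worsened on treatment, and the planned shift table cannot fully separate them. This requires an LLN above 1.5 ×10⁹/L.

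The size estimate depends wholly on the assumed distributions. The effect falls mainly on Grade 1 and hardly touches Grades 3–4. The documents do not support calling it a biased safety analysis or a misreported incidence. It is a cheap improvement of minor consequence.

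**What to change.** In the Neutrophils paragraph of SAP 4.7.2:

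- Keep the worst-grade summary, but lay it out as a cross-tabulation of baseline grade (0–4, with 0 meaning at or above the lower limit of normal) by worst post-baseline grade, for each treatment group.
- Add one row giving the number and percentage of subjects whose worst post-dose grade exceeds their baseline grade.
- State that the pre-dose Day 1 count is baseline and is not part of the on-treatment minimum. SAP 4.5 counts treatment duration from Day 1 and the schedule notes put all blood draws before dosing, so the present wording leaves this open, although the first post-baseline window in SAP Table 3 starts on Day 2.

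The cost is a sentence or two of SAP text and one table, from counts already collected. The worsened-grade row will show slightly fewer cases than the any-grade total, and the cross-tabulation shows where the difference lies. Nothing is hidden, and no eligibility or treatment rule changes.

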4.7.3. Vital Signs

All vital signs including weight, pulse rate, body temperature, respiration rate, and systolic and diastolic blood pressure will be summarized. Descriptive statistics will be presented for the observed value and the change from baseline by treatment and visit if applicable. For repeated assessments at a visit, the average of these values will be taken for the summary at the visit. A data listing of vital signs will also be provided.

4.7.4. Electrocardiogram

Numeric 12-lead ECG parameters will be presented for observed value and change from baseline at Week 12/EOT visit for each Cohort for the following parameters:

- Heart Rate
- QRS
- QT
- QTc
- PR

Number and percent of subjects with normal, not clinically significant abnormal, and clinically significant abnormal results for the 12-lead ECG will be tabulated by Cohort. Incidence of a normal to abnormal shift for overall ECG interpretation from baseline to worst post baseline will also be summarized. For repeated assessment, if interpretations are the same, the last value will be taken for numerical assessment for summaries. If interpretations are different, the last value with the abnormal interpretation will be used for summary.

[figure not shown]
QT interval corrected for heart rate using Fridericia's method - Below incidence will be summarized:

- QTcF interval >500 msec
- QTcF change from the baseline (pre-dose) is >60 msec

All ECG data will be listed in a by-subject listing.

4.7.5. Physical Examination

Clinically significant new or worsened physical examination abnormalities following treatment will be recorded as AEs and will be reflected in the summary of AEs.

4.9. Pharmacokinetic (PK) Analysis

For all subjects, serum samples will be collected at time points indicated in the Schedule of Activities in Appendix 8.1.

Serum concentrations of KPL-404 and derived PK parameters (C_{max} and AUC_{0-t}) will be summarized using descriptive statistics by cohort and day/timepoint. Descriptive statistics will include arithmetic mean, standard deviation, minimum, median, maximum, geometric mean, and geometric coefficient of variation, as appropriate.

Individual listings of serum concentrations and PK parameters will be provided.

Where data are available, KPL-404 dose proportionality will be examined between the dose groups. The $AUC_{0-\infty}$, AUC_{0-t} , and C_{max} estimates will be tested for dose proportionality using a power model approach or analysis of variance (ANOVA) model as appropriate. Where data are available, exposure of KPL-404 administered by SC injection will be compared across dose levels. Scatter plots of PK parameters versus dose or log-dose will also be considered to assess dose proportionality. Log-transformed $AUC_{0-\infty}$ and AUC_{0-t} estimates will be analyzed using an ANOVA model with group as a fixed effect. Other analytical tests may be employed depending on the characteristics of the dataset.

The PK analysis plan and report will be prepared separately.

4.10.	

5. INTERIM ANALYSIS

An interim analysis for Cohort 3 may be conducted to support internal decision-making, for example, when at least 50% of subjects in Cohort 3 have completed the 12-week treatment period. The interim analysis may include cumulative safety, tolerability, PK, clinical response (e.g., DAS28-CRP), and Sponsor will provide the Sponsor decide to conduct an Interim Analysis for Cohort 3, the Sponsor will provide the specifics of the interim analysis plan prior to such analysis as well as the list of individuals who received unblinded data prior to final database lock and formal unblinding of the study. The purpose of the interim analysis is to obtain early information for internal planning of subsequent KPL-404 development. The data from the interim analysis will not be communicated to the study team engaged in daily activities, to investigational sites, or to enrolled subjects until all subjects have completed the study and database lock has been achieved.

To maintain the overall probability of a type 1 error (i.e., alpha) at the specified 0.05 level, the Bonferroni-adjusted Haybittle-Peto method has been chosen as the alpha-spending function which assigns alpha=0.001 to the interim analysis, and 0.049 to the final analysis of the primary efficacy endpoint.

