8.4. Randomization

All subjects who are eligible for study participation will be randomized on Day 1 prior to study drug administration. Each subject will be randomized to receive KPL-404 or placebo as per the randomization schedule prepared before the study by the Sponsor or designee. Randomization will be stratified by available documented evidence of prior inadequate response to ≤ 1 versus ≥ 2 classes of advanced targeted therapy (bDMARD or tsDMARD; e.g., TNF inhibitors, IL-6 receptor inhibitors, T-cell costimulatory inhibitors, anti-CD-20 antibodies, JAK inhibitors).

For Cohorts 1 and 2, subjects will be randomized 3:1, KPL-404 to placebo.

The overall randomization ratio in Cohort 3 is 1:1:1 (5 mg/kg q2wk, 5 mg/kg qwk, placebo). To maintain blinding, the placebo volume will be matched to the corresponding 5 mg/kg volume, and all subjects will be required to attend weekly visits through the treatment period.

The overall randomization ratio in Cohort 4 is 3:2 KPL-404 (600 mg loading dose at baseline followed by maintenance dosing 400 mg q4wk at Week 4 and Week 8) to matched placebo (equivalent volume; SC q4wk; loading dose at baseline followed by maintenance dose at Week 4 and Week 8).

An Interactive Response Technology (IRT) system will issue a unique randomization code to each subject, which will assign the treatment to the subject. The study drug will be assigned, prepared, and administered according to instructions in the Pharmacy Manual.

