1.5. Determination of Sample Size

The sample size for Cohorts 1 and 2 are based on safety and PK considerations.

The sample size for Cohort 3 is based on a 2-sample t-test assuming an improvement in DAS28-CRP change from baseline (CFB) for the KPL-404 being 1.2 points better than placebo (KPL-404 group CFB improvement = 2.2 points, placebo group CFB improvement = 1.0 point, standard deviation = 1.3). With 21 subjects in each of the 3 treatment groups (KPL-404 5 mg/kg qwk, KPL-404 5 mg/kg q2wk, and placebo) having completed 12 weeks of DAS28-CRP assessments, there is 83% power for the treatment comparison of active vs. placebo with 2-sided 0.05 type 1 error. In order to maintain this level of power after accounting for an anticipated discontinuation rate of 16%, up to 25 subjects per treatment group and up to a total of 75 subjects would need to be enrolled in Cohort 3.

The sample size for Cohort 4 is based on a 2-sample t-test assuming an improvement in DAS28-CRP change from baseline for the KPL-404 being 1.3 points better than placebo (improvement for placebo = 1.0 point, standard deviation = 1.3). Enrollment of 22 subjects into the KPL-404 arm and 14 subjects into the placebo arm (i.e., 3:2 randomization ratio) allows 80% power for the treatment comparison with 2-sided 0.05 type 1 error if all subjects complete 12 weeks of DAS28-CRP assessments. In order to account for an anticipated discontinuation rate of 10%, approximately 24 subjects (KPL-404) and 16 subjects (placebo) for a total of approximately 40 subjects are required to enroll under Cohort 4.

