3. GENERAL STATISTICAL CONSIDERATIONS

All analyses and summaries will be produced using SAS® version 9.4 (or higher).

For inferential statistical analyses, each treatment group of KPL-404 will be compared to placebo. Unless otherwise specified, all tests will be at two-tailed using pre-specified level of significance 0.05.

Descriptive statistics (n, mean, standard deviation [SD], median, Q1, Q3, minimum, and maximum) will be presented for continuous variables. For continuous efficacy endpoints, least square (LS) mean, LS mean difference, standard error (SE), and 95% confidence interval (CI) will be calculated.

For categorical variables (including binary variables), counts and percentages will be presented. For binary efficacy endpoints, 95% CI for difference in proportion and p-values will be presented.

Time to event data will be analyzed using the Kaplan-Meier (KM) method, which will include the estimated median with 95% confidence interval (CI) and the 25th and 75th percentiles.

Subject listings for all randomized subjects will be provided for all efficacy and safety data. In general, the subject listings will be sorted by cohort, treatment group, subject number and assessment date (and time, if applicable).

For Cohorts 1 and 2, pooled data will be analyzed by treatment group. Data from Cohorts 3 and 4 will be analyzed separately.

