4.6.1. Multiplicity Adjustment

As this is a phase 2 study, there is no multiplicity adjustment planned for the comparisons of multiple dose levels of KPL-404 versus placebo.

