4.6.2. Analyses of Primary Efficacy Endpoint

The primary analysis for the efficacy endpoints will be based on the mITT population.

The following null hypothesis (H0) and alternative hypothesis (H1) will be tested for each KPL-404 dose against placebo:

- H0: No treatment difference between KPL-404 and placebo.
- H1: There is a treatment difference between KPL-404 and placebo.

The primary estimand for the primary endpoint is defined in Table 1, using the hypothetical strategy.

The intercurrent event that is deemed to have an impact on the interpretation of the variable of interest is treatment discontinuation or using any rescue medications. Data will be set to missing values after occurrence of any intercurrent event prior to Week 12, and the subject's last post baseline observation before the intercurrent event will be carried forward (LOCF) to impute missing endpoint value (for subjects whose postbaseline values are all missing, the baseline will be used to impute). Missing data at Week 12 will be imputed with LOCF method. Analysis of covariance (ANCOVA) models will be used to compare the change from baseline in DAS28-CRP at Week 12 for each of the KPL-404 dose groups and placebo. Baseline value and stratification factor will be included as covariates in the ANCOVA model. The least square (LS) mean of each treatment group, LS mean differences (each KPL-404 group vs. placebo), their standard errors and two-sided 95% CIs, and the nominal p-values for treatment differences will be obtained from the model. No testing between the two KPL-404 dose groups will be conducted.

Sensitivity Analysis (As-Observed Analysis)

The data collected after the intercurrent event will be included in the sensitivity analysis to evaluate the robustness of the primary analysis results with respect to the method of handling data while treatment discontinuation or taking the rescue medications (treatment policy strategy). In addition, for subjects discontinuing the study treatment before Week 12, their off-study treatment values measured up to Week 12 will be included in the analysis. There is no imputation for missing data at Week 12.

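### Does the 0.001/0.049 interim split in SAP section 5 overstate error control, given that Cohort 3 tests two KPL-404 regimens against one placebo arm?

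*SAP*

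**What the plan says.** SAP section 5 allows an optional interim analysis of Cohort 3, for internal planning of later development. It opens the alpha statement with "To maintain the overall probability of a type 1 error (i.e., alpha) at the specified 0.05 level" and then adopts a Bonferroni-adjusted Haybittle-Peto rule that "assigns alpha=0.001 to the interim analysis, and 0.049 to the final analysis of the primary efficacy endpoint".

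The other relevant statements are these:

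- **Allocation (protocol 8.4):** "The overall randomization ratio in Cohort 3 is 1:1:1", with one placebo arm serving both 5 mg/kg regimens (weekly and every two weeks).
- **Hypotheses (SAP 4.6.2):** the null hypothesis "will be tested for each KPL-404 dose against placebo", and "the nominal p-values for treatment differences will be obtained from the model".
- **Multiplicity (SAP 4.6.1):** because the study is phase 2, "there is no multiplicity adjustment planned for the comparisons of multiple dose levels of KPL-404 versus placebo".
- **Test level (SAP 3):** unless stated otherwise, "all tests will be at two-tailed using pre-specified level of significance 0.05".
- **Sample size (SAP 1.5):** with 21 completers per group, "there is 83% power for the treatment comparison of active vs. placebo with 2-sided 0.05 type 1 error".

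**The concern.** The word 'overall' in section 5 carries no qualifier. The split is assigned to the primary efficacy endpoint, and in Cohort 3 that endpoint carries two tests. Section 5 neither says that the control is per comparison nor refers back to 4.6.1. Someone who reads section 5 alone could conclude that the chance of any false positive on the Cohort 3 primary endpoint is held at 5%.

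That would matter because Cohort 3 is the proof-of-concept part of the study. A natural conclusion from it is that at least one regimen works, and the error rate of that statement is nearer 9% than 5%. Protocol 11.2 also has the SAP go to regulators before unblinding, so a formal error claim in it should be one the design delivers.

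**Working it through.** **Inputs.** Levels 0.001 and 0.049 (SAP 5); two-sided tests (SAP 3); two comparisons with placebo (SAP 4.6.2); 1:1:1 allocation (protocol 8.4); interim when at least 50% of Cohort 3 has completed treatment (SAP 5). The exact interim timing is open, so I take information fractions of 0.5 and 0.75.

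**1. The SAP's own figure.** 0.001 + 0.049 = 0.05. This is the Bonferroni bound over two looks at one comparison, and it reproduces the stated level. The sum already uses the whole 0.05. Four tests (two looks, two doses) at these levels would sum to 0.10. The split is therefore built for one comparison over two looks.

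**2. One comparison, both looks.** The critical values are 3.291 (0.001) and 1.969 (0.049). The correlation between looks is √t, where t is the information fraction.

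Error = 1 − P(|Z₁| < 3.291 and |Z₂| < 1.969)

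- t = 0.5 (correlation 0.707): 0.0492
- t = 0.75 (correlation 0.866): 0.0490

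Both are below 0.05, so the claim is true per comparison.

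**3. Two doses, final analysis only.** With equal arms and a shared placebo, the correlation between the two contrasts is 0.5. With neither regimen working:

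P(at least one positive) = 2α − P(both positive)

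- α = 0.049: 0.098 − 0.0090 = 0.0890
- α = 0.05, no interim: 0.100 − 0.0093 = 0.0907

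**4. Two doses, both looks.** Testing each dose at 0.001 at the interim and 0.049 at the end gives 0.0894 (t = 0.5) and 0.0890 (t = 0.75). A simulation of three-arm t tests (1,000,000 trials, interim at about half the subjects) gives 0.0885 with 21 per arm and 0.0894 with 25 per arm.

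**5. Where the excess comes from.** The any-dose error is 0.0907 with no interim and 0.0894 with the split at t = 0.5. The interim rule contributes none of the excess. All of it comes from making two unadjusted comparisons, which is the subject of 4.6.1 and not of section 5.

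**6. Which 0.05 is being protected.** Section 5 refers to a level already specified. The sample size calculation shows what that level attaches to. For 21 per group, a difference of 1.2 and SD 1.3, the noncentrality is 1.2 / (1.3 × √(2/21)) = 2.991 on 40 degrees of freedom. Power at two-sided 0.05 is then 0.831, which is the stated 83% for one regimen against placebo. At 0.025 per dose the same calculation gives 74%, so the design was not sized for control across doses.

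**7. Side by side.** Sections 1.5, 3 and 4.6.2 each attach 0.05, or a nominal p-value, to a single comparison with placebo. Section 4.6.1 says nothing is done across doses. Section 5 names two looks and does not mention doses. Reading 'overall' as across looks agrees with all of these; reading it as across doses contradicts 4.6.1.

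**The case for a change.** The strongest case for a change is that a formal error statement should be right as it stands, without help from other sections. Section 4.6.1 says that no adjustment is made but gives no resulting rate, and section 5 then uses unqualified language about an endpoint that covers both doses. If control per comparison was meant, stating it costs nothing; if control across doses was meant, the plan does not achieve it.

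Part of this stands. Section 5 does leave the scope of its claim unstated, and the 0.09 figure is correct. The second possibility, however, is ruled out by 4.6.1, which addresses the across-dose question under its own heading and declines to adjust. A reader could be misled only by passing over that section and the word nominal in 4.6.2.

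Adding the 0.09 to the SAP would also need care. It applies to the primary endpoint alone and assumes that neither regimen works. ACR20, ACR50 and ACR70 are also tested for each dose without adjustment (SAP 1.3.1.2 and 4.6.3). A bare statement that the chance of a false positive in Cohort 3 is about 0.09 would therefore itself claim too much.

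**Conclusion.** No change follows. The 0.001/0.049 split keeps the type 1 error of each dose-versus-placebo comparison at 0.049 over the two looks, which is what a sentence about dividing alpha between an interim and a final analysis promises. The any-dose error of 0.089 to 0.091 is real, but it results from the disclosed phase 2 choice not to adjust across doses and would be there without an interim.

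The SAP sets no rule under which Cohort 3 succeeds if at least one dose is positive, so no decision in the plan runs at the 0.09 level. The choice is also a fair trade-off: full control across doses at 0.025 each would lower power with 21 completers per group from 83% to 74%. Naming the comparison in section 5 would be tidier, but analysts will apply 0.001 and 0.049 to each comparison either way, and every test, threshold and result stays the same.

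The figures assume equal arms, a shared placebo (correlation 0.5), neither regimen effective, the split applied to each dose separately, and an interim between 50% and 75% of the data. They are insensitive to that timing. Cohort 4 has its own placebo arm and separate analysis, and is not included.
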